Objectives:	
Primary Objective:
 
Efficacy The primary endpoint is to estimate the proportion of patients that are alive and off systemic immunosuppression therapies (IST) at 12 months following initiation of treatment. To meet this endpoint, patients need to remain off IST (e.g. sirolimus, tacrolimus, steroids, etc). for at least 8 weeks. The use of rituximab and ibrutinib are not considered IST for this endpoint.
 
Secondary Objectives:
 
Efficacy
 
To estimate:
 
 1. Chronic GVHD response (CR + PR, both individual organ response and overall response, according to 2014 NIH Response Criteria Working Group Report) – See Appendix G. 2. Cumulative steroid exposure (total mg methylprednisolone or equivalent). 3. Time to discontinuation of systemic immunosuppression, defined as the date that all systemic IST such as sirolimus, tacrolimus, steroids, etc. have been discontinued after resolution of all reversible manifestations of cGVHD. The use of rituximab and ibrutinib are not considered IST for this endpoint. Discontinuation of immunosuppressive medications for the purpose of inducing an anti-tumor response after the development of recurrent or secondary malignancy will not be counted as successful discontinuation of IST.

	
 4. Failure-free survival (defined as being alive without the requirement for second-line cGVHD therapy). See section 6.3 for definition of second-line cGVHD therapy. 5. Non-relapse and overall mortality 
Safety
 
To estimate:
 
 1. Incidence of grade ≥ 3 adverse events, possibly or probably related to either ibrutinib and/or rituximab.
Study Design:	This is an open-label, Phase 2 study designed to evaluate the safety and efficacy of ibrutinib and rituximab as primary treatment of cGVHD.
Population:	35 patients
Centers:	One
Inclusion Criteria: Refer to Section 4 for the complete and detailed list of inclusion/exclusion criteria.	
 1. First episode of systemic immunosuppression-requiring cGVHD, defined as classic or overlap cGVHD by the NIH consensus criteria. 2. Previously untreated cGVHD, defined by having received < 10 days of corticosteroids or alternative systemic immunosuppressive agent started specifically for a new diagnosis of cGVHD. 3. Age ≥ 18 years 4. Karnofsky performance status $\geq 70\%$ 5. Patient willing and able to provide informed consent 6. Adequate hematologic function defined as: 
 • Absolute neutrophil count (ANC) $\geq 1.0 \times 10^9/L$ and off growth factor support for 7 days. • Platelet count $\geq 30 \times 10^9/L$ and no platelet transfusions for 7 days. 7. Adequate hepatic function as defined by: 
 • Total bilirubin of $\leq 1.5 \times$ ULN (unless of non-hepatic origin or due to Gilbert's Syndrome) or • Total bilirubin of $> 1.5 \times$ ULN to $3.0 \times$ ULN if due to cGVHD. 8. Women of childbearing potential and men who are sexually active with a woman of childbearing potential must be practicing a

	highly effective, preferably user-independent method of birth control (failure rate of <1% per year when used consistently and correctly) during treatment and for up to 90 days after the last dose of ibrutinib, consistent with local regulations regarding the use of birth control methods for subject participating in clinical studies.
Exclusion Criteria: Refer to Section 4 for the complete and detailed list of inclusion/exclusion criteria.	Active uncontrolled infection History of HIV infection Active HBV or HCV infection. Subjects who are positive for hepatitis B core antibody, hepatitis B surface antigen (HBsAg), or hepatitis C antibody must have a negative polymerase chain reaction (PCR) result before enrollment. Those who are PCR positive will be excluded Inability to tolerate oral medications. Progressive or recurrent malignancy following allogeneic transplant 1. Known severe or life-threatening hypersensitivity to ibrutinib or rituximab Uncontrolled hypertension Known bleeding disorder Major surgery within 4 weeks of first dose of study drug History of stroke or intracranial hemorrhage within 6 months prior to enrollment Unable to swallow capsules Subjects with chronic liver disease and hepatic impairment meeting Child-Pugh Class C (Appendix D). Female subjects who are pregnant, or breastfeeding, or planning to become pregnant while enrolled in this study or within 90 days of last dose of study drug. Male subjects who plan to father a child while enrolled in this study or within 90 days after the last dose of study drug. Unwilling or unable to participate in all required study evaluations and procedures Unable to understand the purpose and risks of the study and to provide a signed and dated informed consent form (ICF) and authorization to use protected health information (in accordance with national and local subject privacy regulations) Exposure to BTK inhibitor following transplant. Prior exposure to BTK inhibitor pre-transplant is allowed. Vaccinated with live, attenuated vaccines within 4 weeks of first dose of study drug Unresolved toxicities from prior anticancer therapy, defined as having not resolved to Common Terminology Criteria for Adverse Event (CTCAE, v5.0), Grade ≤ 1, or to the levels dictated in the inclusion/exclusion criteria with the exception of alopecia

	
Any life-threatening illness, medical condition, or organ system dysfunction that, in the investigator's opinion, could compromise the subject's safety or put the study outcomes at undue risk
 
Currently active, clinically significant cardiovascular disease, such as uncontrolled arrhythmia or Class 3 or 4 congestive heart failure as defined by the New York Heart Association Functional Classification; or a history of myocardial infarction, unstable angina, or acute coronary syndrome within 6 months prior to study entry
 
Subject who received a strong cytochrome P450 (CYP) 3A inhibitor within 7 days prior to the first dose of ibrutinib or subject who requires continuous treatment with a strong CYP3A inhibitor (Appendix C), with the exception of voriconazole or posaconazole which are permitted on study with appropriate dose modification.
 
Subjects who have received prior treatment with extracorporeal photopheresis (ECP) for cGVHD.

Study Treatment:	
 1. Ibrutinib 420mg PO QDAY (28-day cycles) for a total of 12 cycles (dose adjustment required in patient with hepatic impairment or those receiving concomitant voriconazole or posaconazole or other strong CyP 3A4 inhibitor). 2. Rituximab 375mg/m² IV weekly x 4 weeks (to be started on study day 7 ± 3 days), then 375mg/m² IV q3months x 4 doses (months 4, 7, 10, 13).
Concomitant Therapy:	
 1. Sirolimus (target level 4-10 ng/mL) – patients currently receiving a calcineurin inhibitor (tacrolimus or cyclosporine) and/or mycophenolate mofetil for GVHD prophylaxis will be converted to sirolimus per institutional guidelines. In the case of contraindication or intolerance to sirolimus, another systemic immunosuppressive (IS) drug (i.e. tacrolimus or cyclosporine) may be substituted at the discretion of the treating investigator. 2. Short-course corticosteroids may be used, if necessary, for more rapid symptom control (≤1mg/kg Medrol, with planned taper to be completed no longer than 4 weeks).
Statistical Methods/ Data Analysis: Refer to Section 10 for additional details.	
This is a phase II trial evaluating the safety and efficacy of ibrutinib and rituximab as primary treatment of cGVHD. We plan to enroll 35 patients on this study. Patients will be formally monitored for 12 months to evaluate for outcome and safety endpoints. All patients, responders and treatment failures, will be followed for a period of one year. The primary outcome measure will be the proportion of patients that are alive and off systemic immunosuppression therapies (IST) at 12 months following initiation of treatment. Secondary outcome measures will be cGVHD response, cumulative steroid exposure, time to discontinuation of systemic immunosuppression, requirement for second-line GVHD therapy, non-relapse and overall mortality, and safety.

Sample Size Determination	
The study will be powered to detect a clinically meaningful improvement in treatment success at 12 months post-treatment, defined as being alive and off all systemic immunosuppression. Experience from our phase II study of rituximab in the upfront treatment of cGVHD found that 56% of patients were alive and free of systemic immunosuppression at 12 months post treatment. It is hoped that under this protocol, this rate will be at least 75%. Thus we statistically formalize this study by testing the null hypothesis that p, the treatment success rate is 0.55 or less versus the alternative hypothesis that p is at least 0.75. A sample size of 35 patients gives 80% power with an $\alpha=0.05$, using the formula for a one sample binomial (one-sided) test of a proportion.

----------------------------------	--

ABBREVIATIONS

AE	adverse event
AESI	adverse events of special interest
ALT	alanine aminotransferase
ANC	absolute neutrophil count
ASCO	American Society of Clinical Oncology
AST	aspartate aminotransferase
AUC	area under the concentration-time curve
BCR	B-cell receptor
BTK	Bruton's tyrosine kinase
CLL	chronic lymphocytic leukemia
C _{max}	maximum observed plasma concentration
CR	complete response
CrCl	creatinine clearance
CRF	case report form (paper or electronic as appropriate for this study)
CT	computed tomography
CTCAE	NCI Common Terminology Criteria for Adverse Events
CYP	cytochrome P450
DMC	Data Monitoring Committee
ECOG	Eastern Cooperative Oncology Group
ECG	electrocardiogram
EDC	electronic data capture
FDA	Food and Drug Administration
GCP	Good Clinical Practice
HBsAg	hepatitis B surface antigen
HBV	hepatitis B virus
HCV	hepatitis C virus
HIV	human immunodeficiency virus
HIPAA	Health Insurance Portability and Accountability Act
IAC	Interim Analysis Committee
IB	Investigator's Brochure
IC ₅₀	concentration that inhibits a process by 50%
ICF	informed consent form
ICH	International Conference on Harmonisation
ILD	interstitial lung disease
IEC	Independent Ethics Committee
INR	International normal ratio
IRB	Institutional Review Board
IVRS	interactive voice response system
IWRS	interactive web response system
LDH	lactate dehydrogenase
MCL	mantle cell lymphoma
MedDRA	Medical Dictionary for Regulatory Activities
MRD	minimal residual disease
MRI	magnetic resonance imaging
MRU	medical resource utilization

MTD	maximum tolerated dose
PCR	polymerase chain reaction
PD	progressive disease
PET	positron emission tomography
P-gp	P-glycoprotein
PK	pharmacokinetics
PML	progressive multifocal leukoencephalopathy
PR	partial response
PRO	patient-reported outcome(s)
aPTT	activated partial thromboplastin time
PT	prothrombin time
QTc	QT interval corrected for heart rate
SAE	serious adverse event
SCARs	severe cutaneous adverse reactions
SJS	Stevens-Johnson syndrome
SLL	small lymphocytic lymphoma
t _{1/2}	half-life
T _{max}	time to maximum plasma concentration
TEAE	treatment-emergent adverse event
TLS	tumor lysis syndrome
ULN	upper limit of normal

1. **BACKGROUND**

1.1. **Chronic GVHD**

1.1.1. **Chronic GVHD Background**

Chronic GVHD (cGVHD) is the most important cause of late morbidity and mortality after allogeneic stem cell transplantation, occurring in up to 60% of long-term survivors(Higman and Vogelsang 2004; Schmitz, Eapen et al. 2006; Bhatia, Francisco et al. 2007; Abou-Mourad, Lau et al. 2010) With the increasing number of allogeneic transplants using peripheral blood stem cells (PBSCs), mismatched and unrelated donors and the increasing age of transplant recipients, cGVHD will continue to be a serious challenge following allogeneic transplantation. Chronic GVHD requires therapy for many months and often years(Vogelsang 2001; Koc, Leisenring et al. 2002) and is the cause of death in up to one third of all long-term survivors after transplantation for leukemia(Ratanatharathorn, Ayash et al. 2001). In addition to the effects on mortality, moderate-to-severe cGVHD markedly reduces quality of life (Sutherland, Fyles et al. 1997; Chiodi, Spinelli et al. 2000; Kiss, Abdolell et al. 2002; Fraser, Bhatia et al. 2006). Despite its prevalence and importance, an effective treatment strategy for cGVHD has been difficult to achieve due to the heterogeneous nature of the problem and the lack of clear evidence for the majority of treatment options.

Standard immunosuppressive therapy (IST) for cGVHD using glucocorticoids with a calcineurin inhibitor has not changed in several decades even though most patients respond inadequately. If the total time to discontinue all systemic IST is measured as a surrogate for allograft tolerance, it takes a median of 2-3 years from the onset of cGVHD therapy depending on stem cell source and other factors(Stewart, Storer et al. 2004). Unfortunately, despite the relationship between cGVHD and reduced relapse risk, the prolonged duration of cGVHD makes it the leading cause of infection, morbidity, and late treatment-related deaths (Sullivan, Witherspoon et al. 1988; Wingard, Piantadosi et al. 1989; Syrjala, Chapko et al. 1993; Duell, van Lint et al. 1997; Sutherland, Fyles et al. 1997; Socie, Stone et al. 1999). Furthermore, the widespread and sometimes irreversible manifestations of cGVHD may negatively impact quality of life even after tolerance is achieved. New approaches to the treatment of cGVHD are needed to achieve early control of cGVHD manifestations and facilitate tolerance.

The morbidity and mortality associated with chronic GVHD is caused not only by cGVHD-associated immunodeficiency and organ dysfunction, but also by the immunosuppressive medications used treat it. Long-term glucocorticoid treatment impairs immune function and can therefore increase the risk of opportunistic infections. Other glucocorticoid therapy-related complications include avascular necrosis, glucose intolerance, hypertension, weight gain, changes in body habitus, cataracts, osteoporosis, myopathy, and disturbances of mood and sleep. Attempts to improve upon corticosteroids and a calcineurin inhibitor as initial therapy for cGVHD have been unsuccessful.

1.1.2. B cell depleting therapy for the treatment of cGVHD utilizing Rituximab, an anti-CD20 monoclonal antibody.

Failure to improve cGVHD therapy may be partly attributed to an incomplete understanding of the pathophysiology of cGVHD. Chronic GVHD was traditionally thought to be mediated by donor-derived, alloreactive T cells, although studies have not consistently shown a favorable impact of T-cell depletion on cGVHD (Champlin, Passweg et al. 2000; Pavletic, Carter et al. 2005). There is now mounting evidence implicating B cells in the pathophysiology of chronic GVHD. Antibodies to Y chromosome-encoded minor histocompatibility antigens are generated after sex-mismatched allogeneic transplantation (Miklos, Kim et al. 2004) and the presence of these antibodies has been correlated with the occurrence of cGVHD (Miklos, Kim et al. 2005). The findings led to the hypothesis that an anti-B-cell monoclonal antibody may be an effective therapy for cGVHD. Clinical studies have subsequently confirmed the efficacy of rituximab in steroid-refractory cGVHD with objective responses noted in 50-70% of patients, allowing tapering, and in some cases withdrawal of immunosuppressant therapy (Ratanatharathorn, Ayash et al. 2003; Canninga-van Dijk, van der Straaten et al. 2004; Cutler, Miklos et al. 2006; Okamoto, Okano et al. 2006; Zaja, Bacigalupo et al. 2007). Early evidence also suggests a role for rituximab during the early post-transplant period for prevention of cGVHD (Cutler, Kim et al. 2013; Sauter, Barker et al. 2014).

In a completed phase II trial, our group tested rituximab in the upfront treatment of patients with cGVHD, and the results of this study were recently published in *Biology of Blood and Marrow Transplantation: Corticosteroid-Free Primary Treatment of Chronic Extensive Graft-versus-Host Disease Incorporating Rituximab* (Solomon, Sizemore et al. 2015). We hypothesized that the early use of rituximab would allow for more rapid discontinuation of immunosuppression while obviating the need for long courses of systemic corticosteroids, which would translate into reduced treatment-related morbidity and mortality associated with cGVHD.

Twenty-five patients (median age 56 years [range 29 – 77]) with extensive cGVHD were enrolled on a prospective phase II trial at our institution. Enrollment was limited to patients with first onset extensive cGVHD requiring systemic immunosuppression and without residual or concurrent acute GVHD. All patients received Rituximab 375mg/m² x 4 weekly doses, then one dose q3months x 4 doses. Twenty-two of 25 patients (88%) responded to treatment. Of the 22 responding patients, median time to maximum response was 161 days (range 35 – 300 days) with maximum response being complete in 21/22 patients and partial in 1 patient. Corticosteroids were used sparingly or not at all in the majority of patients. Immunosuppression was discontinued in 17 of 22 evaluable patients (77%) with median time to discontinuation of 300 days (range 138 – 488 days). With a median f/u of 27 months, estimated 2-year overall survival is 82%. Following immunosuppression discontinuation, cGVHD did recur in 7 patients after a median of 166 days (range 21-393 days), requiring reinstitution of systemic immunosuppression. When patients were analyzed 12 months following treatment initiation, 56% were alive, free of active GVHD, and off all systemic immunosuppression.

1.1.3. Targeting the Bruton's tyrosine kinase (BTK) and IL-2 inducible T-cell kinase (ITK) pathways with Ibrutinib for the treatment of cGVHD

BTK and ITK are enzymes responsible for the phosphorylation and activation of downstream effectors in the B-cell receptor (BCR) signaling and T cell receptor (TCR) signaling pathways, respectively. Murine studies suggest that both BTK and ITK are required for the development of cGVHD and that ibrutinib treatment can ameliorate cGVHD severity (Dubovsky, Flynn et al. 2014). Similar to murine studies, CD4 T cells and B cells appear essential in humans for the induction of cGVHD (Cooke, Luznik et al. 2017). Ibrutinib is a potent inhibitor of both BTK and ITK that impairs both B-cell and T-cell function. In response to these preclinical findings, ibrutinib was studied in a phase II trial in 42 steroid-refractory cGVHD patients (Miklos, Cutler et al. 2017). This study demonstrated an overall response rate of 67%, with a durable response at ≥ 20 weeks and ≥ 32 weeks of 71% and 48% respectively. Five of the 28 responders discontinued corticosteroids entirely. Based on the results of this trial, ibrutinib received FDA approval in August 2017 for the treatment of adult patients with cGVHD following the failure of 1 or more lines of systemic therapy.

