2.2. Secondary Objective(s)

Efficacy

To estimate:

- Chronic GVHD response (CR + PR, both individual organ response and overall response, according to 2014 NIH Response Criteria Working Group Report) – See Appendix G.
- Cumulative steroid exposure (total mg methylprednisolone or equivalent).
- Time to discontinuation of systemic immunosuppression (defined as the date that all systemic IST has been discontinued after resolution of all reversible manifestations of cGVHD. Discontinuation of immunosuppressive medications for the purpose of inducing an anti-tumor response after the development of recurrent or secondary malignancy will not be counted as successful discontinuation of IST).
- Failure-free survival (defined as being alive without the requirement for second-line cGVHD therapy). See section 6.3 for definition of second-line cGVHD therapy.
- Non-relapse and overall mortality

Safety

To estimate:

- Incidence of grade ≥ 3 adverse events, possibly or probably related to either ibrutinib and/or rituximab.

- To evaluate the safety and tolerability of combination of rituximab and ibrutinib versus the historical experience with rituximab alone in the upfront treatment of cGVHD.

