7.1.1.5. Adverse Events

The accepted regulatory definition for an adverse event (AE) is provided in [Section 11.1](#). The occurrence of an AE at the time the ICF is signed until first dose should be recorded under medical history in the eCRF form. All medical occurrences after the first dose with study drug

until 30 days after the last dose of study drug that meet the AE definition below must be recorded as AEs in the CRF.

- Grade 1 adverse events do not need recorded
- Grade 2 unexpected **and** possibly/probably/definitely related
- Grade 3 requiring hospitalization **and** unexpected/expected regardless of relationship
- Grade 3 unexpected without hospitalization **and** possibly/probably/definitely related
- All grades 4 & 5 regardless of unexpected/expected or relationship

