10.4. Efficacy Analysis Methods

This is a phase II trial evaluating the safety and efficacy of ibrutinib and rituximab as primary treatment of cGVHD. Efficacy and safety endpoints will be estimated according to the cumulative incidence and Kaplan-Meier methodology in the presence of competing risks. Outcomes will be compared to historical values based on the Gray's test and log rank test respectively. We plan to enroll 35 patients on this study. Patients will be formally monitored for 12 months to evaluate for outcome and safety endpoints (efficacy/safety visits at the completion of month 1, 2, 3, 6, 9, and 12). All other assessments will be done at the physician's discretion or institutional standards. All patients, responders and treatment failures, will be followed for a period of one year. The primary outcome measure will be the proportion of patients that are alive and off all systemic immunosuppression at 12 months following initiation of treatment. The primary endpoint will be estimated according to the Kaplan-Meier methodology in the presence of competing risks. Outcome will be compared to historical values based on the log rank test. Secondary outcome measures will be cGVHD response, cumulative steroid exposure, time to discontinuation of systemic immunosuppression, requirement for second-line cGVHD therapy, non-relapse and overall mortality, failure-free survival and safety. Secondary survival endpoints will be estimated according to the Kaplan-Meier methodology in the presence of competing risks, and outcomes will be compared to historical values based on the log rank test. Secondary time-to-event endpoints will be estimated according to cumulative incidence methodology, and outcomes will be compared to historical values based on the Gray's test (Gray 1988).

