11.1.4. Causality (Attribution)

The investigator is to assess the causal relation (i.e., whether there is a reasonable possibility that the study drug(s) caused the event) using the following definitions:

Not Related: Another cause of the AE is more plausible; a temporal sequence cannot be established with the onset of the AE and administration of the investigational product; or, a causal relationship is considered biologically implausible.

Unlikely: The current knowledge or information about the AE indicates that a relationship to the investigational product is unlikely.

Possibly Related: There is a clinically plausible time sequence between onset of the AE and administration of the investigational product, but the AE could also be attributed to concurrent or underlying disease, or the use of other drugs or procedures. Possibly related should be used when the investigational product is one of several biologically plausible AE causes.

Related: The AE is clearly related to use of the investigational product.

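### The only listed safety endpoint depends on open-label attribution to either of two drugs, so it is not a like-for-like basis for the planned comparison with rituximab alone; an all-cause measure should carry any comparison

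*Combined protocol and SAP*

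**What the plan says.** The synopsis and Section 10.2.2 each list a single item under safety: the incidence of grade 3 or higher "adverse events, possibly or probably related to either ibrutinib and/or rituximab". The synopsis asks only for an estimate. Section 2.2 adds a second safety objective: "To evaluate the safety and tolerability of combination of rituximab and ibrutinib versus the historical experience with rituximab alone". Section 10.4 covers efficacy and safety endpoints together and says: "Outcomes will be compared to historical values based on the Gray's test and log rank test respectively". No other safety endpoint is tied to that objective.

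The synopsis describes the design thus: "This is an open-label, Phase 2 study designed to evaluate the safety and efficacy". It names one centre and no concurrent control. On causality, Section 11.1.4 says: "The investigator is to assess the causal relation"; no independent adjudication is described.

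Section 7.1.1.5 sets the CRF recording rules. One line reads: "All grades 4 & 5 regardless of unexpected/expected or relationship". Grade 3 events that lead to hospitalisation are also recorded whatever their relationship to study drug. No endpoint listed under safety uses these records without the attribution filter.

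**The concern.** A drug-related incidence combines two things: how often severe events occur, and how often the investigator ascribes them to a study drug. In the earlier trial described in Section 1.1.2, rituximab was the drug under test. Here an event counts if it is ascribed to rituximab or to ibrutinib. The share of events called related can therefore differ between the studies even if the underlying event rate does not.

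The population makes attribution hard. Section 1.1.1 describes immunodeficiency caused by cGVHD itself and says: "Long-term glucocorticoid treatment impairs immune function and can therefore increase the risk of opportunistic infections". Steroids in this trial are meant to be short-course, but patients also take sirolimus or a substitute. Section 1.2.1.2 lists infections, some fatal, among the risks of ibrutinib. A severe infection will often have several candidate causes, and whether it enters the endpoint is an unblinded decision.

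At stake is the safety conclusion on a two-drug combination given upfront. An apparent excess over rituximab alone, or an apparent absence of one, could partly be a product of labelling.

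**Working it through.** **The plan's own figure.** The documents give no rate, target or precision for safety. The sample size of 35 comes from the primary efficacy test (Section 10.3). It reproduces with the normal approximation: [1.645 × √(0.55 × 0.45) + 0.842 × √(0.75 × 0.25)]² / 0.20² = 34.97, rounded up to 35. It matters here only as the denominator.

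**The definitions side by side (Section 11.1.4).** One route to Not Related is: "Another cause of the AE is more plausible". Possibly Related is to be used when the drug is one of several biologically plausible causes, including underlying disease and other drugs. An infection in a patient with cGVHD on sirolimus can satisfy both. The second definition leans towards inclusion, but nothing says which prevails.

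**How attribution enters the measure.** With one qualifying event per affected patient, related incidence = all-cause incidence × share attributed. All inputs below are assumptions; none is in the documents. The true incidence is set equal in both studies.

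| All-cause incidence, both studies | Share attributed, this trial | Share attributed, earlier study | Related incidence, this trial vs earlier | Apparent difference |
|---|---|---|---|---|
| 40% | 50% | 30% | 20% vs 12% | +8 points |
| 50% | 50% | 40% | 25% vs 20% | +5 points |
| 50% | 60% | 40% | 30% vs 20% | +10 points |
| 50% | 70% | 40% | 35% vs 20% | +15 points |
| 50% | 40% | 60% | 20% vs 30% | -10 points |

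Across all-cause incidences of 30% to 60% and shares of 30% to 90%, the endpoint could read anywhere from 0.30 × 0.30 = 9% to 0.60 × 0.90 = 54%.

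**Sensitivity to events per patient.** At 40% incidence, 0.40 × 35 = 14 patients are affected. With one event each and 30% to 70% attributed, 4.2 to 9.8 patients are counted, so 9.8 to 4.2 are left out. With two independently judged events each, the chance that at least one is attributed is 1 - 0.7² = 51% to 1 - 0.3² = 91%, so 14 × 0.49 = 6.9 to 14 × 0.09 = 1.3 are left out. The first-row contrast becomes 0.40 × (1 - 0.5²) = 30% against 0.40 × (1 - 0.7²) = 20.4%, or 9.6 points. The omitted count depends strongly on this assumption; the apparent gap in that row does not.

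**What an all-cause measure can deliver.** An observed 14 of 35 has an exact 95% interval of 24% to 58%. For 35 patients against the 25 in the earlier trial (Section 1.1.2), at two-sided 0.05 and 80% power, the detectable rise is about 20% to 55%, or 30% to 66%. Removing attribution removes one bias; it does not make the comparison precise.

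**Whether the data exist.** For this trial they do: grade 4-5 and hospitalised grade 3 events must be recorded under Section 7.1.1.5 and under the broader wording of Section 11.4.1. A full all-cause grade 3 or higher count is less secure, because Section 7.1.1.5 records non-hospitalised grade 3 events only if unexpected and related. For the earlier study, Section 1.1.2 gives no adverse-event rates, collection rule or attribution rule.

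**The case against.** - **A reader might infer that severe infections drop out whenever another cause is available, so an excess would be missed.** The documents do not support that. The Possibly Related definition describes this situation and points towards counting the event. What stands is that the two definitions overlap and the choice is unblinded.
- **A reader might infer that the whole safety assessment rests on attribution.** It does not. Section 10.2.2 lists non-relapse and overall mortality, which needs no attribution to study drug, and Section 10.4 compares secondary outcomes with historical values. Major haemorrhage (Section 11.4.6.1) and new malignancies (Section 11.4.5) are reported with no relatedness condition. But mortality misses non-fatal severe harm, and the other two are reporting duties, not endpoints.
- **The comparator is unseen.** More attribution with two drugs is plausible but unverified, so no direction of bias can be asserted. The same gap affects the remedy: an all-cause comparison needs matching counts from the earlier study, and nothing shows they exist.
- **The comparison is weak whatever the endpoint.** With 35 against 25 non-randomised patients, and no safety hypothesis or threshold depending on it, it can only be descriptive. Section 9.1 also stops adverse-event reporting once new systemic cGVHD therapy is given, which truncates an all-cause count too.

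These objections limit the claim. They do not remove it, because the plan commits to the comparison and, as written, would run it on a measure that mixes toxicity with attribution practice.

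**Conclusion.** The point holds in limited form. The only endpoint listed under safety is not like-for-like with a one-drug study, and inclusion of events with competing causes is left to open-label judgement. A difference from rituximab alone could therefore partly reflect attribution.

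The documents give neither its size nor its direction. The -10 to +15 points are illustrations under assumed incidences and attribution shares with one event per patient; they should not be quoted as an expected bias. Nor do the documents show that the drug-related measure is useless: it remains a reasonable single-arm description.

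This is an inexpensive improvement that should be made. It does not touch the primary analysis or the sample size.

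**What to change.** - **Add an endpoint** in Sections 2.2 and 10.2.2 and the synopsis: the all-cause incidence of grade 4-5 and hospitalised grade 3 events among all treated subjects, with an exact 95% confidence interval and infections shown separately.
- **Keep** the drug-related grade 3 or higher incidence as a descriptive measure.
- **Make the comparison conditional**, and say so in Section 10.4. Compare with rituximab alone only on the all-cause measure, and only if the earlier study's events can be tabulated with the same definition and follow-up window, allowing for the Section 9.1 reporting stop. Label it descriptive. If the condition fails, report the single-arm all-cause estimate without a comparison.
- **Reconcile** the recording rules in Sections 7.1.1.5 and 11.4.1, so that it is clear which grade 3 events reach the CRF.

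The cost is endpoint wording and about one more table for this trial, with no new visits or patients. Any comparison also needs the earlier study's events to be re-tabulated, an effort the documents do not allow one to size. The headline adverse-event rate will be higher than the drug-related rate for the same events.
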